10.1.2 Secondary Endpoint

To determine preliminary efficacy, response (defined as having at least PR in evaluable patients) will be reported as a proportion and 95% confidence interval using exact binomial methods. Given that this is a purely descriptive protocol, there is no set hypothesis regarding the response rate. Proportions for clinical response (defined as having at least PR or stable disease) will also be calculated. Please refer to appendices for detailed explanations of the clinical response criteria for each population.

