10.1.3 Exploratory Endpoints

To describe pharmacodynamic effects, serial measures of megakaryocytes and other hematopoietic cells will be summarized using descriptive statistics such as means, medians and ranges for each time point. These measures will be plotted

for each patient, and these patient specific plots will be plotted for all patients together. Analyses for change over time will be done using repeated measures general linear model analysis.

To evaluate the relationship between biomarker expression levels and response, changes in biomarker expression levels will be related to response using a Wilcoxon rank sum test. To evaluate reduction in splenomegaly by palpation in the MF arm, a categorical variable measuring the extent of splenomegaly will be tracked over time descriptively, since the small sample size will preclude longitudinal analysis. To evaluate improvement in MF symptoms in the MF arm, the Myeloproliferative Neoplasm Symptom Assessment (MPN-SAF) score will be summarized descriptively over time using means, medians, standard errors and ranges.

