Progressive disease ¹¹	
 Appearance of a new splenomegaly that is palpable at least 5 cm below the LCM or A ≥100% increase in palpable distance, below LCM, for baseline splenomegaly of 5-10 cm or A 50% increase in palpable distance, below LCM, for baseline splenomegaly of >10 cm or Leukemic transformation confirmed by a bone marrow blast count of ≥20% or A peripheral blood blast content of ≥20% associated with an absolute blast count of ≥1 × 10⁹/L that lasts for at least 2 weeks
Stable disease	Belonging to none of the above listed response categories.

Relapse	
 • No longer meeting criteria for at least CI after achieving CR, PR, or CI, or • Loss of anemia response persisting for at least 1 month or • Loss of spleen response persisting for at least 1 month
Recommendations for assessing treatment-induced cytogenetic and molecular changes	
Cytogenetic remission	
 • At least 10 metaphases must be analyzed for cytogenetic response evaluation and requires confirmation by repeat testing within 6 months window 
CR: eradication of a preexisting abnormality PR: ≥50% reduction in abnormal metaphases
 
Partial response applies only to patients with at least ten abnormal metaphases at baseline.

Molecular remission	
 • Molecular response evaluation must be analyzed in peripheral blood granulocytes and requires confirmation by repeat testing within 6 months window • CR: Eradication of a pre-existing abnormality • PR: ≥50% decrease in allele burden 
Partial response applies only to patients with at least 20% mutant allele burden at baseline.

Cytogenetic/molecular relapse	Re-emergence of a pre-existing cytogenetic or molecular abnormality that is confirmed by repeat testing.

EMH, extramedullary hematopoiesis (no evidence of EMH implies the absence of pathology- or imaging study-proven nonhepatosplenic EMH); LCM, left costal margin; UNL, upper normal limit.

¹ For all response categories, benefit must last for ≥12 wk to qualify as a response.

² Baseline and posttreatment bone marrow slides are to be interpreted at one sitting by a central review process. Cytogenetic and molecular responses are not required for CR assignment.

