³ Grading of MF is according to the European classification. It is underscored that the consensus definition of a CR bone marrow is to be used only in those patients in which all other criteria are met, including resolution of leukoerythroblastosis. It should also be noted that it was a particularly difficult task for the working group to reach a consensus regarding what represents a complete histologic remission.

⁴ Immature myeloid cells constitute blasts + promyelocytes + myelocytes + metamyelocytes + nucleated red blood cells. In splenectomized patients, <5% immature myeloid cells is allowed.

⁵ See above for definitions of anemia response, spleen response, and progressive disease. Increase in severity of anemia constitutes the occurrence of new transfusion dependency or a ≥20 g/L decrease in hemoglobin level from pretreatment baseline that lasts for at least 12 weeks. Increase in severity of thrombocytopenia or neutropenia is defined as a 2-grade decline, from pretreatment baseline, in platelet count or absolute neutrophil count, according to the CTCAE v 4.0. In addition, assignment to CI requires a minimum platelet count of ≥25 000 × 10⁹/L and absolute neutrophil count of ≥0.5 × 10⁹/L.

⁶ Applicable only to patients with baseline hemoglobin of <100 g/L. In patients not meeting the strict criteria for transfusion dependency at the time of study enrollment (see as follows), but have received transfusions within the previous month, the pretransfusion hemoglobin level should be used as the baseline.

⁷ Transfusion dependency before study enrollment is defined as transfusions of at least 6 units of packed red blood cells (PRBC), in the 12 weeks prior to study enrollment, for a hemoglobin level of <85 g/L, in the absence of bleeding or treatment-induced anemia. In addition, the most recent transfusion episode must have occurred in the 28 days prior to study enrollment. Response in transfusion-dependent patients requires absence of any PRBC transfusions during any consecutive “rolling” 12-week interval during the treatment phase, capped by a hemoglobin level of ≥85 g/L.

⁸ In splenectomized patients, palpable hepatomegaly is substituted with the same measurement strategy.

⁹ For the purpose of this study, spleen or liver responses must be confirmed based on palpation/physical examination, or ultrasound if the body habitus is prohibitive, in keeping with standard care.

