(Note: The original criteria mandates the use of imaging studies where a $\geq 35\%$ reduction in spleen volume, as assessed by MRI or CT, is required. Furthermore, a $\geq 35\%$ volume reduction in the spleen or liver, by MRI or CT, constitutes a response regardless of what is reported with physical examination.)

- ¹⁰ Symptoms are evaluated by the MPN-SAF TSS.¹⁷ The MPN-SAF TSS is assessed by the patients themselves and this includes fatigue, concentration, early satiety, inactivity, night sweats, itching, bone pain, abdominal discomfort, weight loss, and fevers. Scoring is from 0 (absent/as good as it can be) to 10 (worst imaginable/as bad as it can be) for each item. The MPN-SAF TSS is the summation of all the individual scores (0-100 scale). Symptoms response requires $\geq 50\%$ reduction in the MPN-SAF TSS.
- ¹¹ Progressive disease assignment for splenomegaly requires confirmation by MRI or computed tomography showing a $\geq 25\%$ increase in spleen volume from baseline. Baseline values for both physical examination and imaging studies refer to pretreatment baseline and not to posttreatment measurements.

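### Appendix II footnote 11 makes spleen progression in MF depend on MRI or CT that the trial does not schedule; read literally, a patient progressing by palpation can count as a clinical response (minor)

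*Combined protocol and SAP*

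**What the plan says.** The progressive disease row of the MF response table in Appendix II lists five criteria. Three are spleen criteria judged by palpation: a newly palpable spleen at 5 cm or more, growth of at least 100% from a baseline of 5–10 cm, and growth of 50% from a baseline above 10 cm. The other two concern blasts in marrow or blood.

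Footnote 11 is attached to that row: "Progressive disease assignment for splenomegaly requires confirmation by MRI or computed tomography", showing a spleen volume at least 25% above baseline. It adds: "Baseline values for both physical examination and imaging studies refer to pretreatment baseline and not to posttreatment measurements".

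Footnote 9 was adapted for this study in the other direction: "spleen or liver responses must be confirmed based on palpation/physical examination", with ultrasound as the fallback where body habitus prevents palpation. The history of changes (Amendment 5) gives limited resources as the reason for not using CT or MRI to assess spleen response.

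The MF schedule in Section 5.1 lists palpation at screening and on day 1 of cycles. It has no MRI, CT or ultrasound row at any visit.

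Stable disease in the same table is the residual category: "Belonging to none of the above listed response categories". Section 10.1.2 uses it as follows: "Proportions for clinical response (defined as having at least PR or stable disease) will also be calculated". Section 6.2 reports response after cycle 6, and Section 2.2 reports best response.

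**The concern.** Spleen improvement is judged by an examination done at scheduled visits. Spleen worsening is judged by a test that the schedule does not include and that needs a scan taken before treatment. A scan ordered later, when progression is suspected, cannot supply the missing baseline. For any patient without a pretreatment scan, three of the five routes to progressive disease are therefore closed.

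The gap has a favourable direction. A patient not classed as progressive drops to the residual category, and that category counts as clinical response. Preliminary efficacy is the only secondary objective, and clinical response is one of its two planned proportions. All 24 patients may be MF patients, so the gap could apply to the whole trial.

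**Working it through.** The plan gives no figure on this point to reproduce. The check is a reading of the rules, followed by simple arithmetic.

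**Step 1. The two spleen rules side by side.**

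| | Spleen response | Spleen progression |
|---|---|---|
| Rule | Footnote 9 | Footnote 11 |
| Confirmed by | Palpation, or ultrasound if needed | MRI or CT, volume up at least 25% |
| Baseline needed | Palpation | Pretreatment scan |
| In Section 5.1? | Palpation: yes | MRI or CT: no |

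**Step 2. One patient traced through.** Suppose the spleen is palpable at 8 cm at baseline and 16 cm on treatment. The increase is (16 − 8)/8 = 100%, which meets the threshold for a 5–10 cm baseline. Without a pretreatment scan, footnote 11 cannot be satisfied, so this is not progressive disease. At that visit complete and partial remission are excluded, because both require a spleen that is not palpable. If there is also no clinical improvement and no blast-based progression, only stable disease is left, and Section 10.1.2 counts it. If the patient had an anaemia or symptom response, clinical improvement might be assigned instead; the plan does not say whether that counts as clinical response.

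**Step 3. Size relative to the table's palpation thresholds.** Let n be the number of evaluable MF patients and k the number who follow the path in Step 2. The plan gives no value for k. The proportion is raised by up to k/n. For k = 1:
- n = 24: 1/24 = 4.2 points
- n = 18: 1/18 = 5.6 points
- n = 12: 1/12 = 8.3 points

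For scale, assume 12 of 24 patients are reported as clinical responses: 50.0%, exact 95% interval 29.1% to 70.9%. Moving one of them to progressive disease gives 11 of 24: 45.8%, interval 25.6% to 67.2%. The shift is small beside the sampling uncertainty.

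**Step 4. Size relative to imaging.** Let q be the share of palpation progressors whom a scan would have confirmed; it is not in the plan and may lie anywhere from 0 to 1. The rule as written overstates the proportion by kq/n. Assigning progression on palpation alone would understate it by k(1 − q)/n. The second error is the smaller one only if q > 0.5.

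**Step 5. Which analysis is affected.** With 21-day cycles, day 1 of cycle x is study day 21(x − 1) + 1.
- *Response after cycle 6 (Section 6.2).* C7D1 is day 127. A patient still assessed then with a qualifying spleen is exposed. The plan does not say how patients who leave earlier are counted, so no claim is made about them.
- *Best response (Section 2.2).* Footnote 1 says: "For all response categories, benefit must last for ≥12 wk to qualify as a response". Whether this governs stable disease is not stated. If it does not, only a patient already qualifying at C2D1 (day 22), the first scheduled palpation after treatment starts, is affected. If it does, only patients qualifying at or before C5D1 (day 85, that is 12 weeks after day 1) and still assessed at 12 weeks are affected.

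**The case against.** The strongest case on the other side has four parts.

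*Little depends on it.* The primary endpoint is safety. The rate of at least partial remission, with its exact interval, cannot be inflated this way, since partial remission requires a spleen that is not palpable. Of the response rate the plan says: "Given that this is a purely descriptive protocol, there is no set hypothesis regarding the response rate". Spleen growth would still be visible to readers, because under Section 10.1.3 "a categorical variable measuring the extent of splenomegaly will be tracked over time descriptively". All of this stands, and it is why the point is minor.

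*The affected group may be empty.* It needs a patient whose spleen has grown markedly, who is still assessed at C7D1, and who has no pretreatment scan and no other category. Section 4.6 lets the investigator stop treatment for any reason, so such patients may already have left. This also stands.

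*Stable disease is an inference.* No rule covers a threshold that is met but never confirmed; such a patient could also be handled as unconfirmed or not assessable. This stands in part. Stable disease is the natural literal reading of a residual category, but the text does not force it.

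*The imaging rule may have been kept on purpose, and palpation may call progression too often.* Footnote 9 is confined to response, nothing forbids a scan, and a patient with an existing pretreatment scan can be classified. That is fair, but it does not help a patient without one. Step 4 shows that palpation is not demonstrably closer to the truth.

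A reader might infer that the trial's efficacy result is inflated, or that patients will be kept on drug past progression. The documents support neither: the first would need a known number of affected patients, and Section 4.6 answers the second.

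**Conclusion.** The conflict in the text is real: footnote 11 sets a confirmation that the schedule cannot supply, while footnote 9 lets the same organ be judged by palpation for response. Followed literally, it can only raise the MF clinical response proportion relative to the table's palpation thresholds, by up to 4.2 points per affected patient at n = 24 and 8.3 at n = 12. The conclusion assumes no pretreatment scan, no other response or blast-based category, and the literal reading of stable disease. The number affected is unknown, probably small and possibly zero. The point matters mainly for response after cycle 6 and little for best response.

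Severity is minor. Confidence is high for the text conflict and moderate for the effect on clinical response. It would go too far to say that the plan misclassifies these patients against the truth. Some would not have been confirmed on a scan, and for them stable disease is correct under the criteria as written; without the scan, the plan cannot tell which they are.

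**What to change.** Amend footnote 11 to mirror footnote 9, for example:

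*In this study, progressive disease by splenomegaly is assigned by the palpation thresholds in the table (by ultrasound if body habitus prevents palpation), confirmed at the next scheduled palpation where available. A patient who meets a threshold and has no later assessment is not counted as stable disease.*

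Keep the MRI/CT requirement as a note on the original criteria, as footnote 9 already does for response. Make the change before responses are categorised, so that sites do not choose between palpation and imaging case by case.

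**Cost.** No imaging and no extra visit are needed. A patient first qualifying at C7D1 has a final category only at the next palpation: C8D1 (day 148) or C9D1 (day 169), three to six weeks later. Which of the two applies to stable patients depends on whether clinic visits fall on even cycles (Section 5.1, footnote m) or odd cycles (Section 4.2). Palpation is not marked at the end-of-treatment visit, so a patient who stops straight after qualifying may have no confirming palpation; the second sentence of the wording covers that case.

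**Downside.** Palpation is less precise than imaging. Some progression calls may be false, and the clinical response proportion may come out slightly lower for that reason. The repeat palpation is meant to limit this. The gain is consistency with footnote 9 and a progression rule the trial can apply.

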Appendix III – CYP 1A2, 2C9, 2C19, 3A4 and UGT 1A1/2/8 Inhibitors and Inducers

CYP 1A2, 2C9, 2C19, 3A4 and UGT1A1/2/8 INHIBITORS				
1A2	2C9	2C19	3A4	UGT1A1/2/8

Strong
 
 fluvoxamine ciprofloxacin 
Weak
 
 cimetidine 
Other
 
 amiodarone efavirenz fluoroquinolones fluvoxamine furafylline interferon methoxsalen mibefradil 	
Strong
 
 fluconazole 
Moderate
 
 amiodarone miconazole 
Other
 
 efavirenz fenofibrate fluconazole fluvastatin fluvoxamine isoniazid lovastatin metronidazole paroxetine phenylbutazone probenicid sertraline sulfamethoxazole sulfaphenazole teniposide voriconazole zafirlukast 	
Strong
 
 fluvoxamine ticlopidine fluconazole 
Moderate
 
 esomeprazole fluoxetine lansoprazole omeprazole voriconazole 
Other
 
 pantoprazole chloramphenicol cimetidine felbamate indomethacin isoniazid ketoconazole modafinil oxcarbazepine probenicid topiramate 	
Strong
 
 indinavir nelfinavir ritonavir clarithromycin itraconazole ketoconazole nefazodone saquinavir telithromycin grapefruit juice 
Moderate
 
 amiodarone aprepitant erythromycin fluconazole verapamil diltiazem 
Weak
 
 cimetidine chloramphenicol boceprevir ciprofloxacin fluvoxamine imatinib mibefradil mifepristone norfloxacin norfluoxetine starfruit telaprevir voriconazole 	
 Atazanavir Indinavir
CYP 1A2, 2C9, 2C19, 3A4 and UGT1A1/2/8 INDUCERS				
1A2	2C9	2C19	3A4	UGT1A1/2/8

Moderate
 
 tobacco Phenytoin 
Other
 
 broccoli brussel sprouts carbamazepine char-grilled meat insulin modafinil omeprazole rifampin 	
Strong
 
 carbamazepine rifampin 
Other
 
 nevirapine phenobarbital St. John's Wort 	
Strong
 
 carbamazepine rifampin 
Moderate
 
 norethindrone prednisone St. John's Wort 	
Strong
 
 carbamazepine phenytoin rifampin St. John's Wort 
Moderate
 
 efavirenz modafinil barbiturates prednisone oxcarbazepine phenobarbital pioglitazone rifabutin 	
 Carbamazepine Nicotine

Note: for full list refer to: <http://medicine.iupui.edu/clinpharm/ddis/main-table/> and <http://www.pharmacologyweekly.com/content/pages/ugt-enzymes-medications-herbs-substrate-inhibitor-inducer>

Reference: Flockhart DA. Drug Interactions: Cytochrome P450 Drug Interaction Table. Indiana University School of Medicine (2007). "http://medicine.iupui.edu/clinpharm/ddis/clinical-table/" Accessed 3/25/15.

Appendix IV – Protocol History of Changes

Original Protocol – June 02, 2015			
Amendment 1 – Aug 14, 2015			
Section(s) Affected	Prior Version	Amendment 1 Changes	Rationale
Section 4.4 (Management of Clinical Events)	1) Did not have explicit description of the possibility of sedation due to the study drug. 2) N/A	1) Included a statement in section 4.4.3 (Central nervous system effects) that potential participants will be explicitly counseled during the consenting process on the possible effects of sedation due to the study drug and advise them against driving or operating heavy machinery after taking the drug. 2) Included a section (section 4.4.4) on clinical management of differentiation syndrome	Based on Clinical deficiencies pointed out by FDA reviewers
Amendment 1 – Aug 14, 2015			
Amendment 2 – Oct 22, 2015			
Section(s) Affected	Prior Version	Amendment 2 Changes	Rationale
Sec 3.1 (Inclusion Criteria for AMKL patients)	3.14 - Prior version included the following organ function tests as an inclusion criteria: adequate bone marrow function; ANC \geq 1500/mm ³ condition; Platelets \geq 100,000/mm ³ ; Hemoglobin > 9 g/dL	3.1.4 - criteria for organ function tests modified to delete the following: adequate bone marrow function ANC \geq 1500/mm ³ condition Platelets \geq 100,000/mm ³ Hemoglobin > 9 g/dL	To broaden the inclusion criteria and make the study available as an option for relapsed/refractory AMKL patients, who otherwise, have extremely limited treatment options.

Sec 3.3.7 (Exclusion Criteria)	3.3.7 - Previous version did not: specify an upper threshold for excluding patients who have had prior allogenic bone marrow transplant and did not set prior solid organ transplant as an exclusion criteria 3.3.24 – Previous version excluded patients who required administration of myeloid growth factors/platelet	3.3.7 – changed exclusion criteria: 1) to set 60 days as an upper threshold for exclusion of patients with prior allogenic bone marrow transplantation. 2) to exclude patients with prior solid organ transplants. 3.3.24 – deleted criteria to exclude patients with a requirement for administration of myeloid growth factors/platelet transfusions.	As in the case of the inclusion criteria (above), changing this exclusion criteria also can help make the study available to this patient population.
Sec 4.2 (Treatment Administration)	For the statement “In order for each”, the previous version did not have specific criteria with respect to cytopenias for MF and AMKL patients	For the statement “In order for each”, the criteria was clarified to be applicable to MF patients. Also clarified the condition for cytopenias in AMKL patients.	For clarity and to ensure that the amended neutrophil and platelet count criteria can help make the study available to this patient population.
Section 5.0 (Study Procedures – Schedule of events 5.1 and 5.2)	N/A	Study table footnotes updated to include the information on windows for baseline testing, which was clarified via Amnd 1 clarification memo dt 09.21.15 that was IRB approved on 10.23.15 Optional buccal swab added to study table for AMKL (sec 5.2)	To integrate clarification memo information into protocol amendment 2. To incorporate optional correlative study described in sec
Sec 9.3 (Processing and Analysis)	N/A	Description of optional correlative study added.	To gain a better understanding of genetic changes underlying the disease.
Amendment 3 – Feb 1, 2016			
Section(s) Affected	Prior Version	Amendment 3 Changes	Rationale
Cover page, Study Summary, Sec 3.0 (Patient Eligibility), Sec 9.2 (Transport/Shipments)	N/A	Adds Mayo Clinic as affiliate site with [name] as the PI and [name] as co-investigator	Mayo Clinic has been approved as an affiliate site

	Amendment 4	April 21, 2016	
Section(s) Affected	Prior Version	Amendment 4 Changes	
Exclusion Criteria 3.3.15	Patients who have a systemic infection requiring IV antibiotic therapy within 14 days prior to registration (or other severe infection) are not eligible.	Patients with an active, uncontrolled systemic infection are not eligible until deemed controlled by the treating physician.	To increase flexibility for inclusion of such patients
Section 5.1 & 5.2 Study procedures Footnote i	Urinalysis with microscopic analysis (+/-2 PD analysis) will be performed days 1, 4, 8, and 15 of cycle 1, days 1 and 15 of cycles 2-6, and then day 1 of all cycles thereafter (a window of +/- 2 days is permitted for all time points).	Removed: (+/-2 PD analysis) Current language: Urinalysis with microscopic analysis will be performed days 1, 4, 8, and 15 of cycle 1, days and 15 of cycles 2-6, and then day 1 of all cycles thereafter (a window of +/- 2 days is permitted for all time points).	Correction of error. PD analysis is not done with urine
Section 5.1 and 5.2	Windows of +/-2 for each cycle was mentioned in the footnotes	Windows of +/-2 is added to each cycle in both table headings itself to increase clarity : e.g Cycle 1(+/-2 days)	For clarity

	Amendment 5	July 12, 2016	
Section(s) Affected	Prior Version	Amendment 5 Changes	Rationale
Inclusion criteria 3.1.8 and 3.2.9	Male patients, even if surgically sterilized (i.e. status post-vasectomy) agrees to use an acceptable method for contraception during the entire study treatment period through 4 months after the last dose of alisertib	Male patients, even if surgically sterilized (i.e. status post-vasectomy) agrees to use an acceptable method for contraception during the entire study treatment period through 120 days after the last dose of alisertib. Likewise, female patients should agree to use acceptable method for contraception during the entire study treatment period through 90 days after the last dose of alisertib.	Per Takeda safety board and current IB
Exclusion Criteria 3.3.22	Patients who have been diagnosed or treated for another malignancy within 3 years prior to registration are not eligible aside from these exceptions : completely resected basal cell carcinoma or squamous cell carcinoma of the skin, an in situ malignancy, or low-risk prostate cancer after curative therapy.	If a patient had a prior MPN that evolved to a blast phase, but with treatment, reverted to Myelofibrosis at the time of screening, these pts are considered eligible at the discretion of the PI, if not considered suitable for stem cell transplantation.	In order to accommodate patients that fall within this disease spectrum


Section 5.1 Study procedures table
	
Footnote J Peripheral blood (25 ml) and/or bone marrow (bone marrow only if done clinically – will collect about 10-20 ml) samples will be collected for determination of alisertib pharmacodynamics (PD studies). Samples will be collected in dark green top tubes at the start of each cycle and at the time of the Day 15 labs, for a maximum of 6 cycles (or 12 samples total)
	
Removed: dark green top tubes. Added: Please refer to laboratory manual for details.
	
To maintain consistency with the lab manual.

Section 5.2
	
Footnote Peripheral blood (25 ml) and/or bone marrow (if done will collect about 10-20 ml) samples will be collected for determination of alisertib pharmacodynamics (PD studies). Samples will be collected in dark green top tubes
	
Removed: dark green top tubes. Added: Please refer to laboratory manual for details
	
To maintain consistency with the lab manual

	
at the start of each cycle and at the time of the Day 15 labs, for a maximum of 6 cycles (or 12 samples total).
		

Section 5.1 and 5.2
	
Windows of +/-2 days for each visit starting from C1D1
	
Windows of +/-1 day for D1D4 and +/- 2 days for all subsequent visits. NO WINDOW FOR C1D1
	
For logistical convenience and to minimize protocol deviation. No window for C1 D1 as it sets up the dates for subsequent visits.

Section 9.0 Correlatives
	
Approximately 25 ml of peripheral blood and 10-20 ml of bone marrow will be collected in dark green top tubes, and labeled with the patient initials, study number, and date of collection. Samples may sit at room temperature until they are picked up or shipped.
	
Approximately 25 ml of peripheral blood and 10-20 ml of bone marrow will be collected in lavender top EDTA tubes and dark green top tubes respectively, and labeled with the patient initials, study number, and date of collection. Samples may sit at room temperature until they are picked up or shipped.
	
To maintain consistency with the lab manual


Appendix II
	
Footnote 9 Spleen or liver responses must be confirmed using imaging studies where a $\geq 35\%$ reduction in spleen volume, as assessed by MRI or CT, is required. Furthermore, a $\geq 35\%$ volume reduction in the spleen or liver, by MRI or CT, constitutes a response regardless of what is reported with physical examination.
 
In the spleen response section of the table: “A spleen response requires confirmation by MRI or computed tomography showing $\geq 35\%$ spleen volume reduction.”
 
In the spleen response section of the table: “A spleen response requires confirmation by MRI or computed tomography showing $\geq 35\%$ spleen volume reduction.”
	
Footnote 9 modified.
 
For the purpose of this study, spleen or liver responses must be confirmed based on palpation/physical examination, or ultrasound if the body habitus is prohibitive, in keeping with standard care.
 
(Note: The original criteria mandates the use of imaging studies where a $\geq 35\%$ reduction in spleen volume, as assessed by MRI or CT, is required. Furthermore, a $\geq 35\%$ volume reduction in the spleen or liver, by MRI or CT, constitutes a response regardless of what is reported with physical examination.)
 
Deleted this criteria
	
Since this study is not performing CT or MRI for assessment of spleen response, due to limited resources.

Previous amendment Summary of changes (dated April 21,2016)	Rationale for each change was not inserted in the Summary of changes.	Rationale inserted for each change in the Summary of changes	Correction of error and to maintain protocol/amendment format and consistency.
Amendment 6 October 12, 2016			
Section(s) Affected	Prior Version	Amendment 6 Changes	Rationale
Section 3.2.5 Eligibility criteria	Adequate bone marrow and organ function for eligibility included ANC ≥1500/mm ³ Platelet ≥100,000/ mm ³	Adequate bone marrow and organ function for eligibility included ANC ≥1000/mm ³ Platelet ≥50,000/ mm ³	Given observations in NU patients, in keeping with consistency of active MF clinical trials in , and to include patients who may have limited treatment options in such situations
Section 4.2 Treatment administration	In order for each new cycle of therapy to begin, criteria that MF patients must meet included: 
 ANC must be ≥ 1500/mm³ Platelet count must be ≥ 75,000/mm³ 	These requirements have been modified to: 
 ANC must be ≥ 1000/mm³ Platelet count must be ≥ 50,000/mm³ Other language in this section modified to align with this change.	In order to the make protocol more specific/explicit, and consistent across the two arms. This is in keeping with the relaxing of the inclusion criteria, and also to be consistent for both MK and AMKL patients

Section 5.1 and 5.2 Urinalysis
	
Urinalysis was scheduled throughout the study
	
Urinalysis to be done only at screening. Related footnotes modified accordingly
	
Beyond screening, there is no use for the urinalysis. There is no correlative study that requires urine.

Section 3.3.2(Eligibility criteria) & Section 4.5.2(Permitted Concomitant medications/treatments)
	
Patients actively receiving hydroxyurea are eligible and may continue to receive hydroxyurea through cycle 1 of protocol treatment.
	
Added Note: If the platelet count remains above 1 million after cycle 1, hydroxyurea can be used at the treating physician's discretion, if the platelets are 1000 x 10⁹/L, or more, or if there are symptoms from thrombocytosis
	
For clarity

Section 9.1
	
Details about blood and bone marrow sample collection.
	
Added language: In addition, following any bone marrow procedure, two unstained slides should be shipped at room temperature to [name] manual has been updated accordingly.
	
For added correlative analysis.

Amendment 7 December 14, 2016			
Section(s) Affected	Prior Version	Amendment 7 Changes	Rationale
Study summary and Section 3.0(eligibility) and 10.2 statistics section	Sample size : 24 total (12 with MF and 12 with AMKL).	24 total (Maximum 24 subjects, regardless of the disease breakdown of MF or AMKL. If all 24 were MF, that would be acceptable)	To accommodate more patients on the MF arm, since there are more patients available for MF than for AMKL.
Section 3.2.2 Inclusion criteria –MF patients	Patients must be intermediate I risk or beyond and meet criteria such as : ineligible for stem cell transplantation.	Modified to state that patients can be either “ineligible or refusal to undergo stem cell transplantation”	For flexibility, so that various scenarios are covered.
Section 5.1, 5.2 and Section 9.1 Schedule of Events tables and Correlative studies section.	Footnote j: Peripheral blood samples to determine pharmacodynamics of alisertib(correlative studies) were to be collected at D1 and D15 of each cycle for a maximum of 6 cycles.	Footnotej:The D15 sample has been made optional. Also, Footnote i reworded in tables in 5.1 and 5.2: “ It is strongly preferred that correlative samples be collected and shipped only on Monday – Thursday (with same day shipment preferred). Friday collections/shipments should be avoided to ensure sample stability. Since these samples are collected on Day 1 of each cycle, it is preferred that Day 1 visits be conducted on Monday through Thursday when correlative samples are being collected. Sites should use the available windows to achieve this. Please contact the QAM if there are any questions.” Same language inserted in Section 9.1	For convenience of patients commuting long distances. To ensure stability of correlative samples

Section 5.1 and 5.2 Schedule of events tables for MF and AMKL arms
	
C1D1 vital signs should be taken before and after dosing.
 
Urinalysis to be done at screening
	
C1D1 vitals to be done pre-dose(+/-30 mins) as well as about 2 hours (+/- 30mins) post-dose.
 
Urinalysis removed from screening tests. Related footnote removed/modified.
	
For clarity and convenience.
 
Urinalysis not required for this study at any point-per PI


Study summary and Section 10. 2 (Statistics)
	
Approximate standard errors for the estimated response rate when the true response rate is 10% are +/- 6% with a sample of 24 patients total, and +/- 9% with a sample of 12 patients in each disease group.
 
Approximately 4 potentially eligible patients are seen per month at both sites
 
DLT language within the statistics section
	
Approximate standard errors for the estimated response rate when the true response rate is 10% are +/- 6% with a sample of 24 patients total, +/- 18% with a sample of 18 patients, +/- 9% with 12 patients and +/- 10% to 12% with 6 patients.
 
Both sites corrected to read 'all sites'
 
Removed DLT language
	
Updated statistics to align with modification to disease allocation of patients.
 
Correction of typographical error(since there are more than 2 sites).
 
Correction of error, since there are no DLTs in this study.

Amendment 8 March 17, 2017			
Section(s) Affected	Prior Version	Amendment 8 Changes	Rationale

Section 4.2 Treatment administration
 
Section 5.1 Schedule of events for MF patients
	
Description of treatment administration
 
Footnote m: statement that lab and exams will be done only on day 1 of Cycle 7 and beyond.
	
Language modified: to state that beyond cycle 6, for MF patients who are stable, they will be asked to come to clinic on D1 of every even cycle and they will be given drug supply for 2 cycles to facilitate this. During these visits, labs and exams will be done as indicated in the schedule. During the odd numbered cycles, outside lab tests (only CBC and CMP) will be ordered. Patients can start their treatment at home only after the treating physician has reviewed the laboratory results and determined that they are able to continue treatment. For these cycles, the study coordinator will contact the patient on/prior to Day 1 to inform them if they can or cannot start the new cycle, and also check compliance regarding study drug intake.
 
A 'D1' added under the Cycle 7+ column
	
To facilitate patient treatment convenience and flexibility.


Section 5.1 Schedule of events for MF patients
	
Footnote f: description of chemistry panel
 
Footnote g: description of DIC screen and coagulation studies.
	
Added note to state that: Beyond Cycle 6, magnesium and phosphate testing is not required(as part of the chemistry panel).
 
Added note to state that: Beyond Cycle 6, PT/INR,aPTT testing is not required.
	
Per PI: These tests are not required after cycle 6. Hence, they have been removed for convenience.

	
Footnote j: Description of blood and bone marrow samples for PD studies.
 
Footnote k: Bone marrow aspirate and biopsy is to be done within 1 year prior to registration(provided the PI confirms the diagnosis and there is no suspicion for acceleration to blast phase), and thereafter only as clinically indicated.
	
Added language to clarify that : “Correlative bone marrow samples should be obtained any time bone marrows are collected as clinically indicated during study participation. At baseline, correlative bone marrow collection is not mandatory for study entry. However, study team should request 3-4 unstained slides from any prior bone marrow testing performed within the last year before study entry”.
 
Number of slides have been increased from 2 to 3-4 slides(described clearly in section 9.1)
 
Footnote k updated to add timepoint C7D1(+/-14 days) to bone marrow aspirate and biopsy.
	
For clarity and convenience

Section 5.1 Schedule of events for MF patients
 
and section 5.2 Schedule of events for AMKL patients
	
Footnote c: Vital signs included supine and standing blood pressure measurement.
 
Footnote g: 3 pt listed as part of DIC screen at baseline.
 
In both tables, row demonstrating ‘samples for PD studies’ which included both blood and bone marrow samples
	
Footnote c: Removed the detail about ‘supine and standing’ from the blood pressure measurement.
 
Footnote g: 3 pt replaced by aPTT.
 
In both tables, this row has been removed and replaced by 2 different rows demonstrating ‘Bone marrow collection for PD studies and ‘Blood collection for PD studies’.
	
Such detail is not required for this study. Hence, removed in order to minimize protocol deviations.
 
For clarity
 
For increased clarity


Section 5.1 Schedule of events for MF patients
 
and section 5.2 Schedule of events for AMKL patients
 
(contd)
	
In both tables, window for signing informed consent not defined.
	
Added footnote v in both tables stating that informed consent should be obtained within 28 days of registration
	
For clarity and convenience

Section 6.2 Secondary endpoints
	
Response at 6 months will be reported for all evaluable patients.
	
Modified to state: “Response after cycle 6 (upon completion of C7D1 marrow) will be reported for all evaluable patients.”
	
For clarity

Section 9.1
	
Details about Correlative sample collection. 10-20ml of bone marrow at multiple timepoints for cycles 1-6. Two unstained bone marrow slides were required following any bone marrow procedure.
	
Language added to clarify :
 
 1. Collection of 10-20ml of bone marrow at multiple timepoints for cycles 1-6. Collection of 3-4 unstained slides whenever a bone marrow collection is done at baseline or within 1 year prior to study entry. 2. Language stating that bone marrow collection for correlative testing is not mandatory for study entry. However, study team should encourage collection of 3-4 unstained slides from bone marrow collected within the last year prior to enrollment. 	
For clarity, convenience and flexibility.

Section 11.5.2 Study management: Other protocol deviations
	
Promptly reportable Non Compliance (PRNC) definitions listed
	
The term Promptly reportable Non Compliance (PRNC) is replaced by Reportable New Information (RNI)
	
Per NU IRB directive

